The end-of-study follow-up visit will occur 3 months (12 weeks) after the last dose of study drug administration (for patients who complete the study and for patients who prematurely discontinue study).

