5.5.10 Discontinuation of study treatment and premature patient withdrawal

Patients may voluntarily withdraw from the study for any reason at any time. They may be considered withdrawn if they state an intention to withdraw, fail to return for visits, or become lost to follow-up for any other reason.

If premature withdrawal occurs for any reason, the investigator must make every effort to determine the primary reason for a patient's premature withdrawal from the study and record this information on the study completion eCRF.

Patients may be withdrawn from the study for any of the following reasons:

- Withdrawal of the informed consent
- Lost to follow-up
- Withdrawal at the investigator's discretion

Patients who discontinue study drug should NOT be considered withdrawn from the study unless one of the previous reasons apply. These patients are required to follow the abbreviated schedule of assessment (see Table 6-2). Patients who discontinue the study drug should be treated according to the best standard of care. Protocol violations should not lead to patient withdrawal unless they indicate a significant risk to the patient's safety.

For patients who are lost to follow-up (i.e., those patients whose status is unclear because they fail to appear for study visits without stating an intention to withdraw), the investigator should show due diligence by documenting in the source documents steps taken to contact the patient (e.g., dates of telephone calls, registered letters). In case of death, a patient will be considered withdrawn from the study.

The appropriate personnel from the site and Novartis will assess whether study treatment should be discontinued for any patient whose treatment code has been broken inadvertently for any reason. Patients who discontinue study treatment should NOT be considered withdrawn from the study. A Study Drug Discontinuation Form should be completed, giving the date and primary reason for stopping study treatment. See Section 6 for the required assessments of these patients after discontinuation of study treatment. The investigator must also contact the IVRS to register the patient's discontinuation from study drug.

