First-dose monitoring		X						
Urinalysis	Х	X	Х	Χ	Χ	Χ	Х	Х
Study drug dispensation		X	Х	Χ	Χ	Χ		
Study drug accountability			Χ	Χ	Х	Х	Х	
Magnetic resonance imaging	Х						Х	
EDSS	Х						Х	Х
MS relapse ^g	X	X	Χ	Χ	Χ	Χ	Χ	Χ
TSQM	X				Χ		Х	
C-SSRS	Х	X		Χ	Χ	Χ	Х	Χ
Adverse events/SAEs	X	X	Χ	Χ	Χ	Χ	X	Χ
Study completion form							X	

Abbreviations: C-SSRS=Columbia-Suicide Severity Rating Scale; ECG=electrocardiogram; EDSS=expanded disability status scale; EOT=end of treatment; FU=follow-up; HSV=herpes simplex virus; MS=multiple sclerosis;

; SAE=serious adverse event;

TSQM=treatment satisfaction questionnaire for medication.

- a. Follow-up will occur 3 months (12 weeks) after the last dose of study drug for all patients.
- b. The ophthalmology examination will include eye history, visual acuity, dilated ophthalmoscopy, and any procedures necessary to assess macular edema. Optical coherence tomography and fluorescein angiography will be done only if needed to confirm macular edema.
- c. Body temperature is collected only at Screening, Visit 7/EOT, and at the follow-up visit.
- d. A 12-lead ECG will be performed before fingolimod and glatiramer acetate administration, and 6 hours after the fingolimod administration only.

e. Patients will be tested for human immunodeficiency virus, varicella zoster virus (as per guidance in Appendix 3), HSV-1, HSV-2, and rubeola virus.

g. Patients should report symptoms indicative of a relapse at a scheduled visit or at any other time and will be instructed to immediately contact the treating physician if they develop new or reoccurring or worsening neurological symptoms. A neurological examination by the independent evaluating physician must be arranged as soon as possible, preferably within 7 days of the onset of symptoms.

Table 6-2 Abbreviated schedule of assessments for patients who discontinue study drug

Period	Off-Treatment						
Visit	5	6	7/EOS				
Month	6	9	12				
Visit window (days)	±5	±5	±5				
MS relapses ^a	Х	Х	Х				
MS treatment/steroids	Х	Х	Х				
Concomitant medications	X	Х	X				
Magnetic Resonance Imaging							
EDSS			X				
TSQM			X				
		.,					
C-SSRS	X	X	X				
Physical exam	X		X				
Ophthalmologic exam ^c			X				
Dermatology examination			X				
Vital signs ^d /body weight	X	X	X				
Pulmonary function tests			X				
Laboratory values	Xe	Xe	Х				
Adverse events	X	X	X				
SAE reporting	Х	Х					

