#### 3.8.5 Safety data cutoff and visit windows for summaries on follow-up set

For safety summaries on the safety set, only data which are within 45 days (5 times the half life of FTY720, 9 days) after the last dose of study drug will be considered.

For safety summaries on the follow-up set, all data (including assessments or events more than 45 days after the last dose of study drug) will be considered.

The visit windows below will be used in summaries on the follow-up set.

- 1) Last assessment on study drug
- 2) Day 1 to 45 after study drug discontinuation

- 3) Month 3 (day 46 to 135) after study drug discontinuation
- 4) Month 6 (day 136 to 270) after study drug discontinuation
- 5) Month 12 (day 271 to 540) after study drug discontinuation

For the visit window 1), last assessment on or before the last dose date will be used. For visit windows 2) to 5), assessments collected during the specified day intervals after the last dose date will be used.

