## 8.1.2 Adverse events

In this section, the term adverse event (AE) will refer to any entry on the adverse events CRFs. All AEs including infections will be coded using the MedDRA dictionary. The MedDRA version 20.0 or higher will be used depending when the study is completed.

Adverse events will be summarized by presenting, for each treatment group, the number and percentage of subjects having any AE by primary system organ class and preferred term. SAEs, death, drug-related AEs, the AEs leading to premature discontinuation of study drug, AEs requiring study-drug dose adjustment or interruption and AEs requiring additional therapy will be presented in a similar format as AEs. Notable events will include death, nonfatal SAEs (including infections), and AEs (including infections) leading to study drug discontinuation. AEs that fulfill the risk search terms (defined in the case retrieval sheet) with RMP risk will be summarized by risk name and lower level terms.

SAEs include death and non-fatal SAEs. All SAEs starting after the first dose date, including those starting more than 45 days after study drug discontinuation, will be included in the summaries on the safety set.

Additionally, occurrence rates of AEs, i.e. occurrence of AEs per 100 patient year by primary organ class and preferred term will be summarized. The occurrence rate of an event is calculated as the number (n) of all such events that patients experience divided by the patient years (Ny), where patient years are calculated as the sum of the number of days on study drug of all patients divided by 365.25. The occurrence of AEs per 100 patient years, which is calculated as n/Ny\*100, will be presented.

AE summaries on the follow-up set will be conducted for the following time periods defined by days relative to study drug discontinuation: days 1 to 45 after study drug discontinuation, day 46 or later after study drug discontinuation.

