#### 8.1.3 Data summaries for AEs

Summaries on the safety set by treatment group include:

- Incidence of AEs by SOC and PT
- Incidence of AEs that fulfill the risk search terms with RMP risk by risk name and level terms
- Incidence of AEs by SOC and PT and severity
- Incidence of deaths by SOC and PT
- Incidence of SAE by SOC and PT
- Incidence of SAEs that fulfill the risk search terms with RMP risk by risk name and level terms
- Incidence of AEs leading to study drug discontinuation by SOC and PT
- Incidence of AEs requiring study-drug dose adjustment or interruption by SOC and PT
- Incidence of AEs requiring additional therapy by SOC and PT
- Incidence of most frequent (>=1% for any group) AEs by PT
- Incidence of AEs related to study drug by SOC and PT
- Occurrence of AEs per 100 patient-years by SOC and PT
- Occurrence of SAEs by SOC and PT
- Occurrence of NSAEs by SOC and PT

Summaries on the follow-up set by treatment group include:

• Incidence of AEs by SOC and PT (days 1 – 45 after study drug discontinuation, and more than 45 days after study drug discontinuation)

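### Follow-up-set AE incidence from day 46 onward is a crude percentage over unequal observation time, so it rises with an arm's early-stopping rate to the extent that stoppers are retained

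*SAP*

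**What the plan says.** - **Periods.** SAP 8.1.2 divides follow-up-set AEs into "days 1 to 45 after study drug discontinuation, day 46 or later after study drug discontinuation". No upper limit is given, and SAP 3.8.5 says that all data are considered on this set.
- **Statistic.** SAP 8.1.3 lists one AE output for the follow-up set, by treatment group: "Incidence of AEs by SOC and PT (days 1 – 45 after study drug discontinuation, and more than 45 days after study drug discontinuation". No rate is listed for this set.
- **Person-time.** The rate per 100 patient-years is listed only under the safety set. Its denominator is on-drug time: "patient years are calculated as the sum of the number of days on study drug of all patients divided by 365.25".
- **Cutoff.** SAP 3.8.5 limits safety-set data to those "within 45 days (5 times the half life of FTY720, 9 days) after the last dose of study drug".
- **Completers.** Protocol 3.1: "The end-of-study follow-up visit will occur 3 months (12 weeks) after the last dose of study drug administration". Table 6-1 gives this visit a window of ±5 days.
- **Early stoppers.** Protocol 5.5.10: "These patients are required to follow the abbreviated schedule of assessment (see Table 6-2". Table 6-2 marks AE collection at Months 6, 9 and 12.
- **Membership.** SAP 3.1 admits safety-set patients who have follow-up visit data or one safety assessment from day 46 after stopping. It sets no minimum or equal length of follow-up.
- **Bounded windows.** SAP 3.8.5 defines follow-up-set windows of days 46–135, 136–270 and 271–540 after stopping. The AE section uses one open period instead.

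**The concern.** A percentage of patients with at least one event depends on how long each patient is watched. In the period from day 46, observation time depends on when the patient stopped drug, and nothing in the planned table adjusts for it. An arm with more early stopping contributes more long-observed patients and can show a higher percentage although its AE hazard is the same.

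At stake is the reading of post-drug safety by arm, which Protocol 9.5.2 gives as the purpose of the follow-up summaries. Equal stopping cannot be taken for granted. Protocol 1.1 reports AE-related drug discontinuation in the earlier placebo-controlled trial of 7.5% on 0.5 mg, 14.2% on 1.25 mg and 7.7% on placebo. Here two oral doses are compared with a daily injection that the treating physician knows about.

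**Working it through.** **1. The plan's own figure.** Five half-lives of 9 days: 5 × 9 = 45 days. This reproduces the cutoff in SAP 3.8.5.

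**2. Completer's time in the later period.** 12 weeks = 84 days, and 84 - 45 = 39 days. With the ±5-day window this is 34 to 44 days. Using the SAP's target day 450 instead, 450 - 360 - 45 = 45 days.

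**3. Early stopper's time in the later period.** For last dose on study day *s*, with AE collection to Month 12 (day 360) or the 12-week visit, whichever is later:

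time = max(360, *s* + 84) - *s* - 45

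| Last dose (study day) | Days in the later period |
|---|---|
| 1 | 314 |
| 30 | 285 |
| 90 | 225 |
| 180 | 135 |
| 276 or later | 39 |

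**4. Average for stoppers (assumption: last dose uniform over days 1–359).** For days 1–275 the time is 315 - *s*, which sums to 275 × 315 - 275 × 276/2 = 48,675. For days 276–359 it is 84 × 39 = 3,276. The mean is (48,675 + 3,276)/359 = 144.7 days, and 144.7/39 = 3.7. The share of stoppers with more than 39 days is 275/359 = 77%.

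**5. Incidence with the same hazard in every arm.** The chance of at least one AE is 1 - exp(-rate × days/365.25). At an assumed 1 first AE per patient-year:

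- Completer: 1 - exp(-39/365.25) = 10.1%.
- Retained stopper, averaged over the stopping days: 30.7%.
- Arm with stopping proportion *d* and retained share *r*: 10.1% + *d* × *r* × (30.7% - 10.1%). Stoppers who are not retained are given the 12-week visit only.

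| First-AE rate per year | Stoppers retained | 15% stopping | 30% stopping |
|---|---|---|---|
| 1 | all | 13.2% | 16.3% |
| 1 | half | 11.7% | 13.2% |
| 1 | a quarter | 10.9% | 11.7% |
| 1 | none | 10.1% | 10.1% |
| 2 | all | 23.7% | 28.2% |
| 0.2 | all | 2.9% | 3.7% |
| 0.05 | all | 0.75% | 0.96% |

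**6. Status of the inputs.** The AE rates, stopping proportions, retention and uniform stopping times are assumptions. The only planning figure in the documents is an overall dropout rate of 15%, not given by arm. The calculation averages over all completers and stoppers and does not model entry to the follow-up set.

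**7. Check of the remedy.** With events divided by off-drug person-time from day 46, arms with 10% and 25% stopping both show 100 per 100 patient-years at this hazard. Over a common window of days 46–84 both show 10.1%. Under the current rule the same arms, fully retained, show 12.2% and 15.3%.

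**The case against.** Several points on the other side stand:

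- **Retention.** Protocol 5.5.10 requires the abbreviated schedule but lets patients withdraw at any time. With half of stoppers retained the illustrated gap halves, and with none retained it disappears.
- **Size.** No stopping rate by arm is given, and the illustrated percentages are not those of the planned table. The table is by system organ class and preferred term, where most rows have low rates. At 0.05 per year the absolute gap between 15% and 30% stopping is about 0.2 points, although the relative distortion is no smaller.
- **Serious AEs.** Protocol 7.2 requires SAE reporting for 30 days after the last dose or last visit, whichever is later. A completer's SAE window then runs to about day 84 + 30 = 114, or 69 days from day 46. The same extension takes the longest stopper to 314 + 30 = 344 days, so the spread falls from about 8-fold to about 5-fold but remains.
- **Other outputs.** SAEs starting more than 45 days after stopping also enter the safety-set summaries, and all safety data are listed, so timing can be inspected. Neither supplies a comparison adjusted for observation time.

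A reader might also infer three stronger things that the documents do not support. Stoppers are not observed for nearly a year inside this period: 359 days is the maximum total time off drug, and 314 is the maximum from day 46. The rise is not automatic, because it needs stoppers with last dose before about day 276 who stay in the study. And no recovery or rebound comparison of days 1–45 with the later period is planned in any objective or SAP section.

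**Conclusion.** The point holds as a reporting weakness in one descriptive safety table. The later period is open-ended and summarised by crude incidence. Completers have about 39 days in it and retained early stoppers up to about 314, and the only planned person-time rate contains no off-drug time.

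The direction of the distortion follows from the rule, given some retention of early stoppers. Its size does not. The gap of 13.2% against 16.3% rests on uniform stopping, 1 first AE per patient-year, 15% and 30% stopping and full retention. With half retained it is about 11.7% against 13.2%.

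No primary or secondary test is affected, and no inference is specified for this set. The change is worth making because it is cheap and uses data already collected.

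**What to change.** 1. For AEs starting on or after day 46 from last dose, report by arm the number of events or patients per 100 off-drug patient-years. Count person-time from day 46 to each patient's last contact. If patients with a first event are counted, end their person-time at that event.
2. Replace the open period with a first window ending at the 12-week follow-up visit (about day 84–90). Show the number of patients and the person-time observed in it. This window is close to common but not identical for all: a completer's visit falls on days 79–89, and a patient can enter the set on one assessment at day 46.
3. Report later AEs separately, for example in the later SAP 3.8.5 windows with the number at risk in each. The 46–135 window alone would not solve the problem, because it still mixes 39 days with up to 135 - 45 = 90.

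The cost is a wording change in SAP 8.1.2 and 8.1.3, one extra rate table and sparser later windows. No new data are needed.

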## 8.1.2.1 Occurrence of SAEs and NSAEs (non-serious AEs)

For the legal requirements of ClinicalTrials.gov and EudraCT, two required tables on on-treatment adverse events which are not serious adverse events with an incidence greater than X% and on ontreatment serious adverse events and SAE suspected to be related to study treatment will be provided by system organ class and preferred term on the safety set population.

If for a same patient, several consecutive AEs (irrespective of study treatment causality, seriousness and severity) occurred with the same SOC and PT:

- a single occurrence will be counted if there is ≤ 1 day gap between the end date of the
  preceding AE and the start date of the consecutive AE
- more than one occurrence will be counted if there is > 1 day gap between the end date of the preceding AE and the start date of the consecutive AE

For occurrence, the presence of at least one SAE / SAE suspected to be related to study treatment / non SAE has to be checked in a block e.g., among AE's in a  $\leq$  1 day gap block, if at least one SAE is occurring, then one occurrence is calculated for that SAE.

The number of deaths resulting from SAEs suspected to be related to study treatment and SAEs irrespective of study treatment relationship will be provided by SOC and PT.

#### 8.1.3 Data summaries for AEs

Summaries on the safety set by treatment group include:

- Incidence of AEs by SOC and PT
- Incidence of AEs that fulfill the risk search terms with RMP risk by risk name and level terms
- Incidence of AEs by SOC and PT and severity
- Incidence of deaths by SOC and PT
- Incidence of SAE by SOC and PT
- Incidence of SAEs that fulfill the risk search terms with RMP risk by risk name and level terms
- Incidence of AEs leading to study drug discontinuation by SOC and PT
- Incidence of AEs requiring study-drug dose adjustment or interruption by SOC and PT
- Incidence of AEs requiring additional therapy by SOC and PT
- Incidence of most frequent (>=1% for any group) AEs by PT
- Incidence of AEs related to study drug by SOC and PT
- Occurrence of AEs per 100 patient-years by SOC and PT
- Occurrence of SAEs by SOC and PT
- Occurrence of NSAEs by SOC and PT

Summaries on the follow-up set by treatment group include:

• Incidence of AEs by SOC and PT (days 1 – 45 after study drug discontinuation, and more than 45 days after study drug discontinuation)

## 8.2 Laboratory data

#### 8.2.1 SI Units

Data summaries will be provided in SI units. The standard conversion tool (UNITCONV) will be used to convert all values in different units to SI units.

## 8.2.2 Clinically notable criteria

Clinically notable criteria are summarized in Table 4-2.

All applicable post-baseline laboratory results will be checked against the respective notable criteria. For a particular notable criterion, a subject will be counted in the notable abnormal category as long as one of the results meets the criterion. Note that a subject can be counted in both low and high abnormal categories.

Protocol No. CFTY720D2312

For some laboratory parameters (as listed in Table 4-3), subjects may have a character value of "<x.x" or "<x" instead of the actual numeric value which are below the lower limit of detections (LLOD). The 50% of the LLOD rule will be applied to transform a character value into a numerical value as specified in Table 4-3. This rule will be applied to all applicable lab values prior to checking against the notable criteria as well as computation of any statistics.

For the laboratory parameters listed in Table 4-4, results will be summarized based on the abnormal criteria which are defined by pre-specified level of abnormality in terms of either LLN or ULN as listed in Table 4-4.

In addition, the patients meeting modified Hy's Law will be included in the summary of newly occurring or worsening post-baseline liver function test abnormalities. The modified Hy's Law biochemical criteria is defined as at least one of (ALT or AST > 3 x ULN) and (total bilirubin >= 2 x ULN) and (alkaline phosphatase < 2 x ULN) at a same visit.

Table 4-2 Criteria for clinically notable abnormalities

RAP Module 3

Laboratory Variable	Standard Units	SI Units
LIVER FUI	NCTION AND RELATED VARIAB	LES
SGOT (AST)	> 82 U/L	> 82 U/L
SGPT (ALT)	> 90 U/L	> 90 U/L
Gamma glutamyl transferase (GGT) (U/L)	> 130 U/L	> 130 U/L
Bilirubin (total)	≥ 2.0 mg/dL	≥ 34.2 µmol/L
Alkaline phosphatase, serum	> 280 U/L	> 280 U/L
RENAL FUNCTION /	METABOLIC AND ELECTROLYT	E VARIABLES
Glucose	≥ 200 mg/dL	≥ 11.11 mmol/L
Creatinine	≥ 2.0 mg/dL	≥ 176 umol/L
Amylase	≥ 300 U/L	≥ 300 U/L
Cholesterol (total)	≥ 240 mg/dL	≥ 6.21 mmol/L
Triglycerides	≥ 300 mg/dL	≥ 3.39 mmol/L
BUN	≤ 2 mg/dL	≤ 0.7 mmol/L
	≥ 30 mg/dL	≥ 10.7 mmol/L
Sodium	< 125 mEq/L	< 125 mmol/L
	> 154 mEq/L	> 154 mmol/L
Chloride	≤ 85 mEq/L	≤ 85 mmol/L
	≥ 119 mEq/L	≥ 119 mmol/L
Potassium	≤ 3.0 mEq/L	≤ 3.0 mmol/L
	≥ 6.0 mEq/L	≥ 6.0 mmol/L
Magnesium	≤ 1.0 mg/dL	≤ 0.40 mmol/L

RAP	Mod	dule	3

	≥ 3.00 mg/dL	≥ 1.23 mmol/L
Calcium	≤ 7.5 mg/dL	≤ 1.87 mmol/L
	≥ 11.6 mg/dL	≥ 2.89 mmol/L
Phosphate	≤ 2.0 mg/dL	≤ 0.65 mmol/L
	≥ 5.3 mg/dL	≥ 1.71 mmol/L
	HEMATOLOGY VARIABLES	
Haemoglobin	≤ 10.0 g/dL	≤ 100 g/L
Platelets (Thrombocytes)	≤ 100 k/mm³	≤ 100 x 10  /L
	$\geq$ 600 k/mm 	≥ 600 x 10  /L
<labeled (direct)="" as="" count="" database="" in="" platelet=""></labeled>		
Leukocytes (WBCs)	≤ 2.0 k/mm³	≤ 2.0 x 10  /L
	$\geq$ 15 k/mm $^3$	≥ 15 x 10  /L
<labeled (total)="" as="" database="" in="" wbc=""></labeled>		
HEMA	TOLOGY VARIABLES: DIFFERENTIA	AL
Granulocytes (Poly, Neutrophils)	≤ 1,000 /mm³	≤ 1 x 10  /L
	$\geq 12000/\text{mm}^3$	≥ 12 x 10  /L
<labeled (seg.="" +
Bands)></labeled>		
Lymphocytes	< 200/mm³	< 0.2 x 10  /L
	$\geq$ 8000/mm 	≥ 8 x 10  /L
Red blood cells (RBCs)	< 3,300,000/mm 	< 3.3 x 10  /L
	> 6,800,000/mm 	> 6.8 x 10  /L

\*"Americas" refers to North (Canada, US), Central, and South America. It is applicable only to Canada and US in this study.

Table 4-3 The lower limit of detections of laboratory parameters

Laboratory test	Character value	50% Lower limit of detection (LLOD)
Absolute Monocytes	ABSMON < 0.1	ABSMON= 0.05 x 10  /L
Absolute Lymphocytes	ABSLYM < 0.1	ABSLYM = 0.05 x 10  /L
Alkaline Phosphatase	ALKPHS < 3	ALKPHS = 1.5 U/L

Amylase	AMY < 3	AMY= 1.5 U/L
SGOT (AST)	SGOT < 5	SGOT = 2.5 U/L
SGPT (ALT)	SGPT < 4	SGPT = 2 U/L
Gamma Glutamyltransferase (GGT)	GGT < 5	GGT = 2.5 U/L
Bilirubin (total)	TBIL < 2	TBIL = 1 μmol/L
Bilirubin (direct/conjugated)	DBIL < 3	DBIL = 1.5 μmol/L
HCG	HCG < 2	HCG = 1 IU/L
Herpes Simplex Virus 2 lgG	HSVIGG4 < 0.5	HSVIGG4= 0.25
IgG antibody to varicella zoster virus	IGGVZV2 < 10	IGGVZV2 =5 U/L
Glucose	GLUC < 1 mmol/L	GLUC= 0.5 mmol/L
Urine Protein Dipstick test	UPROTST < 0.1	UPROTST =0.05

